experiences a new onset of fever concomitantly with one or more of the above-mentioned symptoms of protocol-defined ILI (that persists for or reoccurs after a period of at least 12 hours).

The NP swab will be obtained as soon as possible and no later than 7 days (between D0 and D6) from the onset of the ILI.

Reporting of events temporally associated with an ILI

In addition to obtaining an NP swab, the site will collect detailed information about the ILI, as well as information on occurrence of ALRI, otitis media, healthcare utilization events (hospitalizations, emergency room visits, and non-routine office visits [including urgent care visits]) and medication use (eg, antibiotics, antivirals).

In the event that an NP swab cannot be collected, the research site will still obtain the above information. All subjects' parents/guardians reporting a suspected ILI will have a 30-day follow-up telephone call.

Laboratory testing for the confirmation of influenza and determination of similarity to vaccine components

All NP specimens will be submitted for analysis by both culture and PCR, and a positive result on either test will be considered a laboratory-confirmed case of influenza.

Positive cultures or positive PCR samples will undergo additional testing (typing, subtyping, and strain identification, utilizing genetic sequencing) to determine if the virus detected is similar to any of those contained in the vaccine formulation for the respective season.

Note: Positive PCR samples that have negative culture results, or were unable to be expanded in culture, will not undergo additional testing.

Blood sampling

A subset of randomly selected subjects (Immunogenicity Subset) will provide 2 blood samples (5 mL each):

- Previously vaccinated subjects will provide a pre-vaccination (baseline) blood sample at V01 (D0) and a post-vaccination blood sample at V02 (D28 [+7 days]) for HAI testing and potential seroneutralization (SN) and enzyme-linked lectin assay (ELLA) testing.
- Previously unvaccinated subjects will provide a pre-vaccination (baseline) blood sample at V01 (D0) and a post-vaccination blood sample at V03 (28 days after V02 [+7 days]) for HAI testing and potential SN and ELLA testing.

Note: the Re-vaccination Cohort will automatically be part of the Immunogenicity Subset

Collection of safety data

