- 4) Give the subject or subject’s parent / guardian a ruler to measure the size of any injection site reaction, a thermometer for temperature measurement, and instructions on how to use them.
- 5) Remind the subject or subject’s parent / guardian to promptly notify the site in case of an SAE/AESI or ILI symptoms that may occur at any time during the study.
- 6) Schedule Visit 2 (to occur 28 days after Visit 1).
- 7) Complete the relevant CRB forms for this visit.

Visit 2 (Day 28+7): Dose Allocation, Vaccination and Collection of Safety Information

The Investigator or delegate will:

- 1) Collect information on any medications taken during the study period.
- 2) Review and collect completed DC1
- 3) If deemed necessary, perform and document a targeted physical examination per standard site-specific immunization practices and record temperature in the source documents.
- 4) Review temporary and definitive contraindications to vaccination.
- 5) Contact IRT for allocation of unique dose number.

The unblinded qualified study staff member will:

- 1) Administer the appropriate vaccine intramuscularly into the anterolateral muscle of the thigh or the deltoid muscle of the upper arm, as appropriate
- 2) Record the injection site / side / route / dose number and affix the detachable corresponding label in the source documents.

The Investigator or delegate will:

- 1) Keep the subject under medical surveillance for at least 30 minutes after the injection and report the occurrence or non-occurrence of any SAE in the source documents.
- 2) Provide the subjects' parent / guardian with DC2.
- 3) Schedule Visit 3 (to occur 28 days after Visit 2).
- 4) Complete relevant CRB forms for this visit.

Visit 3 (Day 28 + 7 after Visit V02): Post-Vaccination Blood Sample (for Immunogenicity Subset) and Collection of Safety Information

The Investigator or delegate will:

- 1) Collect information on medication taken during the study.
- 2) Review and collect DC2.
- 3) If the subject is part of the Immunogenicity Subset:
 - a. Draw approximately 5 mL of blood sample. Process the blood sample as specified in the "Management of Samples" section (see [Section 7](#)).
Note: If 5 mL of blood sample cannot be drawn, a volume less than 5 mL can be obtained.
- 4) Give the subject's parent / guardian the memory aid to record ILI information (except for subjects in the Re-vaccination Cohort), medications, and SAEs/AESIs, together with instructions for its completion.

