9.4.1.2 Efficacy Assessment Methods

9.4.2 Immunogenicity

9.4.2.1 Immunogenicity Endpoints

Immunogenicity for correlate of protection

- HAI titer for each vaccine strain 28 days after the last vaccination, together with occurrence of an ILI starting \geq 14 days after vaccination, confirmed as positive for any influenza A or B type
- HAI titer for each vaccine strain 28 days after the last vaccination, together with occurrence of an ILI starting \geq 14 days after vaccination, laboratory-confirmed for viral strains similar to those contained in the vaccine

Antibody persistence

For subjects enrolled in both Season 1 (NH) and Season 3 (NH) and who are randomized to the Immunogenicity Subset, the HAI Ab titers against the 4 vaccine strains used in Season 1 (NH) will be measured at D0 before starting vaccination in Season 3 (NH). The following endpoints will be described.

- HAI individual titer on D0 and 28 days after the last vaccination of Season 1 (NH) and on D0 of Season 3 (NH)
- Detectable HAI titer, ie, with a titer ≥ 10 (1/dilution [dil]) at D0 and 28 days after the last vaccination of Season 1 (NH) and on D0 of Season 3 (NH)
- Subjects with titer ≥ 40 (1/dil) on D0 and 28 days after the last vaccination of Season 1 (NH) and on D0 of Season 3 (NH)

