12.2.7 Immunogenicity Analysis Set

The IAS will be used for all descriptive immunogenicity objectives and is defined as the subjects in the main cohort randomized in Immunogenicity Subset and the subjects in the Re-vaccination Cohort in Season 3 who received at least 1 dose of the study vaccine and had one post-vaccination blood sample. Subjects will be analyzed as treated.

For analysis of immunogenicity by NT and ELLA methods, the subset of IAS with available results on the considered serological method will be used.

For correlate of protection assessment, subjects part of both IAS and FASE will be considered.

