5.1.1.2 Statistical Methods

Efficacy

The rVE of QIV-HD relative to QIV-SD will be compared in a step-wise manner:

A non-inferiority testing approach will be applied first, using a non-inferiority margin of -10%. If non-inferiority is demonstrated, a superiority test will be applied using a superiority margin of 5%. Both tests will use a one-sided Type I error at 2.5% if the interim analysis at the end of Season 2 is not performed, and there is no need for multiplicity adjustment due to the step-wise approach.

The rVE of QIV-HD to QIV-SD will be estimated for primary endpoint as follows:

$$rVE = (1 - (C_{HD} / N_{HD}) / (C_{SD} / N_{SD})) \times 100\%$$

where:

- C_{HD} and C_{SD} are the numbers of influenza cases meeting the considered primary endpoint definition in the QIV-HD and QIV-SD groups, respectively.
- For analysis in PPASE, the first episode among those occurring more than 14 days after the last vaccination will be considered. For analysis in FASE, the first episode among those occurring more than 14 days after the first vaccination will be considered.
- If subject experiences multiple occurrences of the same endpoint, only the first episode will be considered
- N_{HD} and N_{SD} are the numbers of subjects in the QIV-HD and QIV-SD groups, respectively.

CIs for rVE will be calculated by an exact method assuming a binomial distribution of the number of cases in the QIV-HD group conditional on the total number of cases in both groups.

The rVE of QIV-HD will be considered as non-inferior to QIV-SD if the lower bound of the rVE is $> -10\%$, and superior to QIV-SD if the lower bound of the CI for the rVE is $> 5\%$. The PPASE will be used as the primary analysis set for the non-inferiority test and the FASE will be used as the primary analysis set for the superiority test.

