5.2.7 Immunogenicity Analysis Set

The IAS will be used for all descriptive immunogenicity objectives and is defined as the subjects in the main cohort randomized in the Immunogenicity Subset in Seasons 1, 2, and 3 and the subjects in the Re-vaccination Cohort in Season 3 who received at least one dose of the study vaccine and had one post-vaccination blood sample. Subjects will be analyzed as treated.

For analysis of immunogenicity by SN and ELLA methods, the subset of IAS with available results on the considered serological method will be used.

For correlate of protection assessment, subjects who are part of both the IAS and the FASE will be considered.

¹ other vaccines, blood products, immune-suppressors, immune-modulators with immunosuppressive properties, anti-proliferative drugs such as DNA synthesis inhibitors

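### As worded, the correlate-of-protection endpoints count influenza that begins before the HAI titre is drawn, which can bias the titre-risk association toward no protection

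*Protocol*

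**What the plan says.** Protocol 9.4.2.1 and the synopsis list two correlate endpoints. Each pairs "HAI titer for each vaccine strain 28 days after the last vaccination, together with occurrence of an ILI starting" at least 14 days after vaccination, one for any influenza A or B type and one for vaccine-similar strains. Neither says whether the 14 days run from the first or the last dose.

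Protocol 5.1.3 sets the sampling times. Previously vaccinated children give a "post-vaccination blood sample at V02 (D28 [+7 days]) for HAI testing"; previously unvaccinated children give a "post-vaccination blood sample at V03 (28 days after V02 [+7 days]) for HAI testing".

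The population is stated in Protocol 12.2.7 ("For correlate of protection assessment, subjects part of both IAS and FASE will be considered") and in SAP 5.2.7 ("For correlate of protection assessment, subjects who are part of both the IAS and the FASE will be considered"). Entry to the immunogenicity analysis set (IAS) needs only children "who received at least 1 dose of the study vaccine and had one post-vaccination blood sample". For efficacy analyses in the FASE, SAP 5.1.1.2 states that "the first episode among those occurring more than 14 days after the first vaccination will be considered". Cases between doses are dropped only in the per-protocol efficacy set (Protocol 12.2.4, SAP 5.2.2), which is not the correlate set.

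Protocol 12.1.3 leaves the exploratory modelling to the SAP. SAP 5.1.3.3, where it appears to sit, is blank in the public copy.

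**The concern.** A correlate analysis asks whether the titre a child carries into the risk period predicts later influenza, so the titre has to come before the outcome. Here the outcome can come first. A child infected between day 14 and the draw may show a titre raised by that infection, yet enters the analysis as a case with a high titre after vaccination. Such cases look like failures despite good antibody levels, and the estimated slope of risk on titre is flattened or, in the extreme, reversed.

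Protocol 1.4 notes that no quantitative correlate of protection is proven in children. The analysis therefore addresses an open question, and the issue bears on its validity and not just its precision.

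**Working it through.** The documents give no sample size, power or effect size for this analysis, so there is no stated figure to reproduce.

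**Step 1. Gap between the start of case counting and the draw.** Inputs: counting from day 14 (Protocol 9.4.2.1; the FASE rule says more than 14 days, a one-day difference); V02 at D28-D35, when dose 2 is given (Protocol 5.1.4.5: "Visit 2 (Day 28+7): Dose Allocation, Vaccination and Collection of Safety Information"); V03 at 28-35 days after V02.

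- 1 dose: draw at D28-D35; 28 − 14 = 14 and 35 − 14 = 21 days.
- 2 doses, last-dose reading: draw 28-35 days after dose 2; again 14-21 days.
- 2 doses, first-dose reading: draw at 28 + 28 = D56 to 35 + 35 = D70; 56 − 14 = 42 and 70 − 14 = 56 days.

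The gap is positive on every reading.

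**Step 2. Is there a readable rule that removes these cases?** The IAS and FASE definitions do not. Surveillance and swabbing run from the first vaccination (Protocol 5.1.3, 5.1.5.1). Protocol 9.4.1.1 has a separate endpoint for influenza between the two injections, so such cases are foreseen. Influenza between doses is not a definitive contraindication in Protocol 5.2.7.2, so such a child can receive dose 2, give the V03 sample and enter the IAS. SAP 4.3 refers back to the protocol for observational endpoints and does not redefine them.

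**Step 3. Share of at-risk time before the draw.** With the draw on day d and an assumed surveillance length S of 120-210 days from dose 1, the share is (d − 14)/(S − 14).

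| | S = 120 | S = 210 |
|---|---|---|
| 1 dose, d = 28 to 35 | 14/106 to 21/106 = 13-20% | 14/196 to 21/196 = 7-11% |
| 2 doses, first-dose clock, d = 56 to 70 | 42/106 to 56/106 = 40-53% | 42/196 to 56/196 = 21-29% |

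These are shares of time. They equal shares of cases only under a constant hazard, and vaccination is planned before the season starts (Protocol 5.1.1), so the share of cases is probably smaller.

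**Step 4. Illustrative effect on the odds ratio (OR).** Logistic regression on simulated data, 300,000 children per setting. All inputs are assumptions: log2 titre SD 2, attack rate 6%, true OR per 2-fold titre of 0.70 or 0.80. The low figure assumes a 4-fold boost in half of the pre-draw cases; the high figure assumes a 16-fold boost in all of them.

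| Cases before draw | True OR 0.70 | True OR 0.80 |
|---|---|---|
| 5% | 0.709 to 0.745 | 0.814 to 0.842 |
| 10% | 0.721 to 0.782 | 0.821 to 0.893 |
| 20% | 0.736 to 0.872 | 0.840 to 0.985 |
| 30% | 0.752 to 0.959 | 0.866 to 1.077 |

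With no boost the estimate stays at its true value (0.695-0.705 and 0.797-0.804). With the pre-draw cases removed it returns to 0.69-0.71 and 0.79-0.81 in every setting.

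**The case against.** The strongest objection is that the text that would settle the matter is redacted. SAP 5.1.3.3 is an empty heading in the public copy. The SAP reference list contains entries on a framework for correlates of protection, the treatment effect explained by a surrogate marker, logistic regression and case-cohort variance, and no readable section cites them. A rule on the risk period could well sit there. This stands. A reader might infer that the SAP contains no such rule, but the documents do not support that. The entry of not applicable in SAP 5.7 does not help either, because a restriction in 5.1.3.3 would be the promised detail and not a change.

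Second, a reader might take the six-week window for 2-dose children as stated. It is inferred. The sentence on the IAS and FASE selects children and does not set the case clock for this endpoint. Protocol 9.4.2.1 says only vaccination, while most of the efficacy endpoints in 9.4.1.1 specify the first. The FASE convention makes the longer window plausible, and the last-dose reading still leaves 14-21 days.

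Third, the size is driven by assumptions. Pre-season vaccination should make the earliest weeks low-risk, an onset a few days before the draw may leave no time for a rise, and infection mainly boosts the infecting strain or a cross-reacting one whereas titres are analysed by strain. This also stands. It limits the size and does not change the direction.

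**Conclusion.** The point holds as one about wording. As written, the correlate endpoints and their analysis set include confirmed influenza with onset before the titre is measured, by at least 14-21 days on any reading and by 42-56 days for 2-dose children on the first-dose clock. If some of those infections raise the titre analysed, the bias is toward no protection; if none do, there is no bias.

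The size cannot be computed from the documents. It depends on the unknown share of early cases and on how many are boosted for the strain analysed. The simulated range, from a shift of about 0.01 in the odds ratio to an estimate near or just above 1, illustrates sensitivity and is not a forecast.

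A reader might conclude that the correlate analysis will give a wrong answer. The documents support only that it can, and only if the redacted section has no restriction. Nor does the point reach the relative efficacy estimates, the confirmatory tests, alpha or the sample size, none of which uses this pairing of titre and outcome. Confidence is moderate and severity low.

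**What to change.** For the correlate endpoints only:

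- Count a laboratory-confirmed ILI only if its onset is after the child's post-vaccination blood sample, and start risk time at that sample.
- Exclude children with confirmed influenza before the sample, or analyse them separately. They should not be recoded as non-cases, since their titres may carry the infection boost.
- Amend Protocol 9.4.2.1, the matching synopsis text and the IAS/FASE sentence in SAP 5.2.7. If SAP 5.1.3.3 already has such a rule, bring the endpoint wording into line with it.

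The change needs no new data, because ILI onset and sampling dates are already collected. The cost is the loss of the early cases from an exploratory analysis limited to the Immunogenicity Subset. That loss is small if few cases precede the draw; if many do, it is a real loss of information, but that is also where the bias would be largest.

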9.4.2.2 Immunogenicity Assessment Methods

Assays will be performed by the Sponsor's laboratory (GCI, Swiftwater, PA, USA) or at an external testing laboratory under GCI supervision. The address is provided in the Operating Guidelines.

A description of the anti-influenza antibody titration by inhibition of hemagglutination is found in [Section 9.3.2.2](#).

9.4.3 Safety

There are no observational safety objectives.

10 Reporting of Serious Adverse Events

To comply with current regulations on SAE reporting to health authorities, the Investigator must document all SAEs regardless of causal relationship and notify the Sponsor and the Clinical Research Associate (CRA) within the notification timelines stated in the following sections. The Investigator will give access and provide the Sponsor and the CRA with all necessary information to allow the Sponsor to conduct a detailed analysis of the safety of the investigational product(s). It is the responsibility of the Investigator to request all necessary documentation (eg, medical records, discharge summary, autopsy) in order to provide comprehensive safety information. All relevant information must then be transcribed onto the AE CRF and the appropriate Safety Complementary Information CRFs.

10.1 Initial Reporting by the Investigator

Serious adverse events occurring during a subject's participation in the study or experiment must be reported within 24 hours to the Sponsor's GPV Department and to the CRA. Every SAE must be reported, even if the Investigator considers that it is not related to the vaccine. The Investigator (licensed physician [M.D. or D.O.]) must validate the information entered on the AE CRF by completing the investigator validation form.

The Investigator must indicate on the AE CRF that the event was serious and must complete the relevant SAE section of this form as well as the appropriate Safety Complementary Information CRFs. An e-mail alert will automatically be sent by the EDC system to the GPV mailbox, the CRA and the GCDSE-V with relevant SAE information details.

If the EDC system is unavailable, the site must notify the Sponsor, using the paper version of the CRB, as described in the operating guidelines.

The Investigator must complete the paper copies of the AE CRF and of the appropriate Safety Complementary Information CRFs and send them to the Sponsor by one of the following means:

- By fax, to the following number: [contact]
- In PDF format to the following e-mail address, using a method of transmission that includes password protection: [contact]
- By express mail, to the following address:

Global PharmacoVigilance, Sanofi Pasteur
[name]
[name]

When the EDC system becomes available, the Investigator must transcribe the information from the paper forms into the EDC system.

If there is need for urgent consultation, the Investigator is to contact the RMO. If the RMO cannot be reached, the Investigator may contact the Call Center as described in [Section 5.3](#).

10.2 Follow-up Reporting by the Investigator

The AE CRF completed initially must be updated within 24 hours after the Investigator has become aware of any new relevant information concerning the SAE (eg, outcome, precise description of medical history, results of the investigation). All relevant information must be included directly in the AE CRF and the appropriate Safety Complementary Information CRFs. An e-mail alert will be sent automatically to the GPV Department and to the CRA. Copies of documents (eg, medical records, discharge summary, autopsy) may be requested by the GPV Department.

The anonymity of the subject must always be respected when forwarding this information.

10.3 Reporting of SAEs Occurring After a Subject Has Completed the Study

Any SAE that occurs after a subject has completed the study but that is likely to be related to the investigational product(s), other products (eg, a benefit vaccine), or to the experiment must also be reported as soon as possible. In such a case, the reporting procedure to be followed is identical to that described in [Section 10.1](#).

10.4 Assessment of Causality

The causal relationship between the SAE and the product administered will be evaluated by the Investigator as described in [Section 9.3.3.3.5](#).

Following this, the Sponsor's Global Safety Officer will also assess the causal relationship to the product, based on the available information and current medical knowledge.

The causal relationship to study procedures will be also assessed in the CRB.

The decision to modify or discontinue the study may be made after mutual agreement between the Sponsor and the Investigator(s).

11.1 Data Collection and CRB Completion

Individual diary cards, specifically designed for this study by the Sponsor and provided to the study sites, will be given to study subjects in the ESafAS for the recording of daily safety, ILI symptoms and associated events, and healthcare utilization described in [Section 9.3.3.3](#). These diary cards will include pre-listed terms and intensity scales (see [Table 9.2](#) and [Table 9.3](#)) as well as areas for free text to capture additional safety information or other relevant details. Subject's parent(s) / guardian(s) in the ESafAS will also be provided with rulers for measuring the size of injection site reactions, and with standard digital thermometers for measuring daily temperatures. To ensure consistency of reporting, the study sites will instruct subjects' parent(s) / guardian(s) on how to correctly use these tools.

The 6-month follow-up will be done by interviewing subjects either during a visit or over the telephone using a questionnaire to capture ILI symptoms, associated events, and healthcare utilization, SAEs, AESIs, and medications if applicable. A memory aid will be provided to the subjects at the preceding study visit to help them record information on events occurring between this visit and the 6-month follow-up.

Relevant information will be transcribed into the AE CRF. Any SAEs captured during this 6-month follow-up period will be reported and followed up as per the normal process for reporting SAEs.

At specified intervals, the Investigator or an authorized designee will interview the subjects' parent(s) / guardian(s) to collect the information recorded in the diary card, and will attempt to clarify anything that is incomplete or unclear. All clinical study information gathered by the study site will be reported electronically by the Investigator or authorized designee using a web-based CRB. (Any information that was not documented in the diary card will first be captured in the source document and then reported electronically.) The CRB has been designed specifically for

this study under the responsibility of the Sponsor, using a validated Electronic Records / Electronic Signature-compliant platform (21 CFR Part 11).

To ensure the correct and consistent completion of the CRBs, the Sponsor or authorized representative will provide all necessary tools, instructions, and training to all site staff involved in data entry prior to study start. Additional instructional documents such as training manuals and completion instructions will be provided to assist with data entry during the course of the study.

Upon completion of training, each user requiring access to the EDC system will be issued a unique username and password. In the event of a change in study personnel, each newly assigned individual will receive a unique username and password; the username and password of a previous user may not be reissued. If any study personnel leave the study, the Investigator is responsible for informing the Sponsor immediately so that their access is deactivated. An audit trail will be initiated in the EDC system at the time of the first data entry to track all modifications and ensure database integrity.

The Investigator is responsible for the timeliness, completeness, and accuracy of the information in the CRBs; must provide explanations for all missing information; and must sign the CRB using an e-signature.

